15.3.8.1. DERIVATIONS

Time to flare will be calculated for each severity as defined in Section 15.1.

Document: SGN35-022 SAP v1 V0.3
Author: [REDACTED]

Version Number: 1.0
Version Date: 31Jan2017

Template No: CS_TP_BS016 – Revision 3
Effective Date: 01Apr2016

Reference: CS_WI_BS005

15.3.8.2. ANALYSIS

The analysis for incidence of flares will replicate that performed for SRI, and will be performed for each severity grade (mild/moderate and severe) and overall.

The flare-free survival function will be estimated by treatment group and for all active-treated subjects combined using Kaplan-Meier methodology, with 95% confidence intervals based on Greenwood's formula. These survival curves will be plotted. The KM estimates of quartiles for time to event with the corresponding 95% CIs will be provided for each treatment and for all active-treated subjects, when estimable, using Greenwood's formula.

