## 4.0 INVESTIGATIONAL PLAN

### 4.1 Summary of Study Design

This is a multicenter, randomized, placebo-controlled, double-blind, multiple-ascending-dose study to evaluate the safety and tolerability of brentuximab vedotin in subjects with active SLE. Approximately 40 subjects in 4 dosing cohorts (10 subjects per cohort) are planned for study participation at approximately 20 study sites in the US. Subjects who meet inclusion and exclusion criteria will be randomly assigned in a 4:1 ratio within each dosing cohort to receive IV brentuximab vedotin or placebo every 3 weeks (Days 1, 22, 43, and 64) for a total of 4 doses. The following doses are planned for each ascending dose cohort:

[figure not shown]
- 0.3 mg/kg IV every 3 weeks for 4 doses;
- 0.6 mg/kg IV every 3 weeks for 4 doses;
- 1.2 mg/kg IV every 3 weeks for 4 doses; and
- 1.8 mg/kg IV every 3 weeks for 4 doses.

There will be a total of 10 subjects in each dose cohort with 8 subjects randomly assigned to each of the 4 brentuximab vedotin doses and 2 subjects to placebo (for a total of 8 placebo subjects overall). Initiation of enrollment at the next dose level will only commence after the final subject of each cohort has been evaluated at the Day 43 visit, and upon endorsement of the SMC following review of the safety data. Depending on the findings, the SMC may recommend additional enrollment of subjects at specific dose levels to better characterize the safety of a particular dose, or may recommend different dose regimens based on the emerging safety data. When available from each full cohort, the SMC will review all Day 85 safety data and may recommend that an already enrolled succeeding dose cohort be discontinued, or its treatment regimen truncated. Doses are not to exceed 1.8 mg/kg IV every 3 weeks or equivalent. Up to 20 subjects total may be enrolled via additional SMC-recommended cohorts for a total of up to 60 subjects.

Assessments for safety (including PML monitoring, see Section 6.3.3), efficacy, PK, and PD will be performed at the times indicated in the schedule of events (see [Table 3](#)). Following the last dose of study drug, there will be a 6-week observation period (through Day 106) and a follow-up visit will take place at Day 127.

A flowchart of the study design is presented in [Figure 1](#).

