### 8.2 Statistical Methods

Data will be analyzed by Quintiles Inc. biostatistical staff. All details regarding the statistical analysis and the preparation of tables, listings, and figures will be described in the Statistical Analysis Plan prepared by Quintiles and approved by the Sponsor before database lock.

Summaries for safety and efficacy data collected will be presented for each treatment group, ie, for brentuximab vedotin 0.3, 0.6, 1.2, or 1.8 mg/kg IV every 3 weeks and placebo at each scheduled visit/assessment. Placebo subjects across cohorts will be aggregated for analysis. Subjects will be evaluated according to the treatment received.

For qualitative parameters, the population size (N for sample size and n for available data) and the percentage (of available data) for each class of parameters will be presented. Quantitative parameters will be summarized by the population size (N for sample size and n for available data), the mean, the standard deviation, the median, 25th percentile, 75th percentile, the minimum, and the maximum values. Geometric means and coefficients of variation will be included as deemed relevant.

A nominal significance level of 5% will be used for exploratory inference testing.

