3. STUDY DESIGN

3.1. GENERAL DESCRIPTION

This is a multicenter, randomized, placebo-controlled, double-blind, multiple-ascending-dose study to evaluate the safety and tolerability of brentuximab vedotin in subjects with active SLE. Approximately 40 subjects in 4 dosing cohorts (10 subjects per cohort) are planned for study participation at approximately 20 study sites in the US. Subjects who meet inclusion and exclusion criteria will be randomly assigned in a 4:1 ratio within each dosing cohort to receive IV brentuximab vedotin or placebo every 3 weeks (Days 1, 22, 43, and 64) for a total of 4 doses. The following doses are planned for each ascending dose cohort:

- 0.3 mg/kg IV every 3 weeks for 4 doses;
- 0.6 mg/kg IV every 3 weeks for 4 doses;

Document: SGN35-022 SAP v1 V0.3
Author: [REDACTED]

Version Number: 1.0
Version Date: 31Jan2017

Template No: CS_TP_BS016 – Revision 3
Effective Date: 01Apr2016

Reference: CS_WI_BS005

[REDACTED]

- 1.2 mg/kg IV every 3 weeks for 4 doses; and
- 1.8 mg/kg IV every 3 weeks for 4 doses.

Individual doses are based on subject weight and will be administered as an IV infusion over approximately 30 minutes. Dose and/or schedule adjustments are not permitted. In-line filters are permitted. However the study drug cannot be mixed with other medications. Further instructions on the dose preparation and administration will be provided in the Pharmacy Manual.

Initiation of enrollment at the next dose level will only commence upon endorsement of the SMC following review of the safety data. Depending on the findings, the SMC may recommend additional enrollment of subjects at specific dose levels to better characterize the safety of a particular dose, or may recommend different dose regimens based on the emerging safety data. When available from each full cohort, the SMC will review all Day 85 safety data and may recommend that an already enrolled succeeding dose cohort be discontinued, or its treatment regimen truncated. Doses are not to exceed 1.8 mg/kg IV every 3 weeks or equivalent. Up to 20 subjects total may be enrolled via additional SMC-recommended cohorts for a total of up to 60 subjects.

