15.2.1.2. ANALYSIS

The following analyses will be performed for all study days with Day 85 specified as the secondary endpoint, and all other visits falling under exploratory analyses.

The percentage of subjects demonstrating SRI Response will be presented by treatment with 95% CI using Wilson's score method (SAS PROC FREQ syntax: table response/binomial (wilson)). Comparisons between each active treatment group and placebo will be performed using Fisher's exact test (two-sided). The ratio of percentages (relative risk) for active to placebo will be presented for each dose level with corresponding 95% CI, based on the score method [Farrington] (SAS PROC FREQ syntax: table trta*response / relrisk(method=score equal)). Percentages with Wilson 95% CI will be plotted versus study day per treatment, with all treatments overlain.

Logistic regression of the log odds of SRI response on log2 dose level (mg/kg) will be performed. Placebo subjects will be treated as a having dose of 0 mg/kg. Based on this model, the estimate of the slope and odds ratio (OR) for a doubling of dose will be presented with 95% CI (based on the profile likelihood) and two-sided p-value (Wald test).

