15.3.13.2. ANALYSIS

The time to treatment failure will be analyzed as detailed for SELENA flares (Section 15.3.8.2).

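### Kaplan-Meier 95% intervals based on Greenwood's formula, in groups of 8, collapse or vanish when a group has no events, and the SAP names no transformation and no rule for that case

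*SAP*

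**What the plan says.** For SELENA flares, SAP 15.3.8.2 first sets the groups: "The flare-free survival function will be estimated by treatment group and for all active-treated subjects combined". As to method, it says that this is to be done "using Kaplan-Meier methodology, with 95% confidence intervals based on Greenwood's formula". Quartiles of time to event also get intervals, but only "when estimable, using Greenwood's formula"; that proviso is attached to the quartiles and not to the survival function. No linear, log or log-log form is named, and nothing is said about a group with no events.

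Sections 15.3.9.2, 15.3.10.2, 15.3.11.2 and 15.3.12.2 refer back to this method. So does 15.3.13.2: "The time to treatment failure will be analyzed as detailed for SELENA flares (Section 15.3.8.2").

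The flare, active renal disease and corticosteroid sections also analyse occurrence in the same way as SRI. For SRI, section 15.2.1.2 says: "The percentage of subjects demonstrating SRI Response will be presented by treatment with 95% CI using Wilson's score method", and gives the SAS option. Section 15.3.13.2 gives treatment failure no such incidence analysis.

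Protocol 4.1 plans "8 subjects randomly assigned to each of the 4 brentuximab vedotin doses and 2 subjects to placebo" in each cohort of 10. Protocol 8.2 adds: "Placebo subjects across cohorts will be aggregated for analysis". SAP 3.1 allows for more: "Up to 20 subjects total may be enrolled via additional SMC-recommended cohorts for a total of up to 60 subjects".

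**The concern.** Greenwood's variance is a sum over observed events, so it is exactly zero until the first event. With 8 subjects and an uncommon event, a whole curve can pass without one. The output would then show either a band of no width labelled 95%, or no band, for a dose tested in 8 people.

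The protocol says the trial should give enough experience to design a larger Phase 2 study. A reader comparing doses for severe or renal flares needs to see how little 8 event-free subjects exclude. For treatment failure the gap is larger, because the Kaplan-Meier interval is the only one planned.

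**Working it through.** **Inputs.** Group size (Protocol 4.1 and 8.2): 10 × 4/5 = 8 per active dose; 2 × 4 cohorts = 8 pooled placebo; all active 4 × 8 = 32. This reproduces the planned sizes. The documents give no event rate, so the event probability by a fixed time is an assumption, varied below. The event-free probability is S = 1 − event rate.

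**Formulas.** Greenwood: Var(S) = S² × Σ d/[r(r − d)], where d is the number of events and r the number at risk at each event time. Without earlier censoring this equals S(1 − S)/n.
- Linear interval: S ± 1.96 √Var.
- Log-log interval: S raised to the power exp(±1.96 q), with q = √(Σ d/[r(r − d)]) / |ln S|.

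**No events in 8.** S = 1 and the sum is 0. Linear: 1 ± 0, so 100% to 100%. Log-log: q = 0/0, so no interval. This is algebra and holds at any n. Wilson for 8 of 8 event-free is 67.6% to 100%; exact is 63.1% to 100%.

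**One event in 8.** S = 0.875 and √(0.875 × 0.125/8) = 0.117. Linear: 0.875 ± 1.96 × 0.117 = 64.6% to 110.4%. Log-log: 38.7% to 98.1%. Wilson: 52.9% to 97.8%.

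**Chance of no events and actual coverage at n = 8** (exact binomial enumeration, no censoring; chance of no events = S⁸):

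| Assumed event rate | No events | Linear | Log-log, undefined counted as a miss | Log-log, when defined | Wilson |
|---|---|---|---|---|---|
| 5% | 66.3% | 33.6% | 27.9% | 83.0% | 94.3% |
| 10% | 43.0% | 56.5% | 53.1% | 93.3% | 96.2% |
| 20% | 16.8% | 82.2% | 77.6% | 93.2% | 94.4% |
| 30% | 5.8% | 93.1% | 88.4% | 93.9% | 94.2% |
| 40% | 1.7% | 84.4% | 93.3% | 95.0% | 93.3% |
| 50% | 0.4% | 93.0% | 96.1% | 96.9% | 93.0% |

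At 60% the linear figure is again 84.4%. If all five groups had a 10% rate, at least one would have no events in 1 − (1 − 0.430)⁵ = 94% of trials.

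**All active, n = 32.** Linear coverage is 80.2%, 84.0% and 89.0% at 5%, 10% and 20%. Log-log, when defined, is 97.5%, 96.3% and 95.9%.

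**Enlargement.** Suppose all 20 extra subjects joined one dose cohort at 4:1 (an assumption). The dose group would be 8 + 16 = 24, and the chance of no events would still be 0.95²⁴ = 29% at a 5% rate and 0.90²⁴ = 8% at 10%.

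**With dropout.** Simulation at n = 8 used 20,000 runs per rate, exponential event times and an assumed 15% dropout by Day 127, evaluated at Day 85. At rates of 5%, 10%, 20% and 30%, linear coverage was 32.6%, 54.5%, 79.9% and 91.5%. Log-log with a Wilson interval (number at risk at Day 85) when no event had occurred gave 94.8%, 96.7%, 95.2% and 95.0%. A Wilson interval on the effective sample size S(1 − S)/Var gave 94.8%, 96.7%, 95.2% and 95.3%.

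**The case against.** A reader might infer that Greenwood intervals at n = 8 fall far below 95% in general. They do not: the large shortfalls need events that are rare, or nearly universal.

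A reader might also infer that the curves would claim certainty, or that the choice of transformation makes no difference. A zero-width band needs the linear form, which the SAP neither names nor excludes. A log-log interval is simply absent at zero events. Where it exists it covers about 93% to 97% at event rates of 10% to 50%, although only 83% at 5%. The low log-log figures in the table come from counting a missing interval as a miss.

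Rarity is assumed, and for some endpoints the definitions point the other way. Corticosteroid use counts any oral use, in a population allowed up to 40 mg/day of prednisone. A mild/moderate SELENA flare needs only one of five criteria. Treatment failure includes increased corticosteroids, while Protocol 5.7.2 permits up to two bursts. Rarity is most plausible for severe and renal flares: eligibility excludes impaired renal function and urgent severe disease, and follow-up ends at Day 127.

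The incidence tables soften the harm, but they need not match the curves under any method. Incidence is by visit among subjects with data, whereas Kaplan-Meier is cumulative and censors. With complete data, though, no events in 8 would read 0% (0% to 32.4%) in one output and, in linear form, 100% (100% to 100%) in the other.

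Finally, these are exploratory, unadjusted analyses; the protocol lists the flare and treatment-failure analyses only as possible additional outcomes. The SRI endpoint is untouched. All of this lowers the weight of the point. It does not supply the missing transformation or zero-event rule, nor an alternative interval for treatment failure.

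**Conclusion.** The point holds for uncommon events. As written, SAP 15.3.8.2 produces a zero-width interval or none whenever a group has no events, and that part needs no assumption. How often this happens, and the coverage figures, rest on assumed event rates, independent subjects and evaluation at a fixed time. At rates of 5% to 20%, linear coverage runs from about 34% to 82% in groups of 8. Pooling all active subjects narrows the gap without closing it. At intermediate rates the matter is minor, and log-log would serve. The consequence is confined to descriptive, exploratory output, most clearly severe and renal flares and, for want of a second interval, treatment failure. It is worth correcting because a 95% label should not sit on an interval of no width, and the repair is cheap.

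**What to change.** In SAP 15.3.8.2, state that intervals for the event-free probability use Greenwood's variance on the log-log scale. For any group with no events, report a Wilson (or exact) interval with the number at risk as denominator, at scheduled visits such as Day 85. With 0 events and 8 at risk, Wilson gives 67.6% to 100%.

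Do not extend this into the tail once final-visit censoring begins. Follow-up has a ±7 day window, so the number at risk falls quickly, and one remaining event-free subject would give 20.7% to 100%. By contrast, a group with one early event and an effective sample size still at 8 would keep 52.9% to 97.8%.

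An acceptable alternative is the Wilson interval on the effective sample size throughout, with the number at risk used when S = 1 and the same limit to scheduled visits. Carry the chosen rule into every section that refers to 15.3.8.2, including treatment failure.

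The cost is a sentence or two in the SAP, a short extra programming step on the Kaplan-Meier output, and wider intervals.

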15.3.9. BILAG SLE FLARES

15.3.9.1. DERIVATION

A moderate flare is defined as ≥ 2 new BILAG B domain scores, relative to baseline. A severe flare is defined as development of any new BILAG A domain score, relative to baseline.

The time to first flare will be derived for each severity above, as detailed in Section 15.1. If a subject experiences both moderate and severe flares during the course of the study, both events will be analysed separately.

The number of domains exhibiting a new A or B score will be determined per subject per study visit.

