    - prednisone  $> 0.5$  mg/kg/day,
    - new immunosuppressive, or
    - increased PhGA to  $> 2.5$ .
- **BILAG SLE flare** definitions include:
  - BILAG flare:
    - development of any new BILAG A domain score, or
    - $\geq 2$  new BILAG B domain scores;
  - BILAG severe flare: development of any new BILAG A domain score.

- **Renal flare** is defined as any of these 3 events:
  - increased proteinuria, as defined by:
    - a urinary protein:creatinine ratio  $> 0.5$ , provided the 24-hour urine protein (if done) contains a total of at least 500 mg of protein, OR
    - a reproducible increase in 24-hour urine protein levels to:
      - $> 1,000$  mg if the baseline value was  $< 200$  mg,
      - $> 2,000$  mg if the baseline value was between 200 and 1,000 mg, or
      - more than twice the value at baseline if the baseline value was  $> 1,000$ ;
  - impaired renal function, as defined by a reproducible decrease in eGFR of  $> 20\%$ , accompanied by proteinuria ( $> 1,000$  mg/24 hours), hematuria ( $\geq 4$  RBCs/hpf or above the reference range for the laboratory), and/or cellular (RBC and WBC) casts; or
  - new hematuria, as defined by a new, reproducible hematuria ( $\geq 11$  to 20 RBCs/hpf) or a reproducible increase in hematuria by 2 grades compared with baseline, associated with  $> 25\%$  dysmorphic RBCs, glomerular in origin, exclusive of menses, accompanied by either an 800 mg increase in 24-hour urinary protein levels or new RBC casts.

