#### **6.2.3.3 Exploratory**

Exploratory efficacy outcomes include the following:

- proportion of subjects achieving a BICLA response at Day 85;
- proportion of subjects achieving a BILAG clinical response at Day 85
- proportion of subjects achieving a BILAG partial clinical response at Day 85, defined as BILAG C scores or better;

- proportion of subjects achieving a BILAG partial clinical response at Day 85, defined as a maximum of 1 BILAG B score or better;
- proportion of subjects achieving a SLEDAI clinical response at Day 85, defined by a  $\geq 4$  point improvement from baseline;
- proportion of subjects achieving organ-specific BILAG clinical response and partial clinical responses at Day 85 as determined by organ domain-specific scores;
- proportion of subjects achieving 20%, 50%, 70%, and n% (ACR20, ACR50, ACR70, and ACRn, respectively) improvement in SJC and TJC at Days 22, 43, 64, 85, 106, and 127;
- mean and median of observed and percentage change from baseline in SLEDAI, CLASI, TJC, SJC, PtGP, PtGA, PhGA, hsCRP, and ESR at Days 22, 43, 64, 85, 106, and 127;
- mean and median of observed and percentage change from baseline in organ domain-specific SLEDAI scores at Days 22, 43, 64, 85, 106, and 127;
- mean and median of observed and percentage change from baseline in HAQ-DI, SF-36, SF-36 Physical Component Summary (PCS), SF-36 Mental Component Summary (MCS), and FACIT-F at Days 43, 85, and 127;
- mean and median of observed and percentage change from baseline in urinary sediment (cellular casts, pyuria, hematuria), proteinuria (protein/creatinine ratio), and eGFR at Days 22, 43, 64, 85, 106, and 127; and
- mean and median of observed and percentage change from baseline in urinary sediment (cellular casts, pyuria, hematuria), proteinuria (protein/creatinine ratio), and eGFR at Days 22, 43, 64, 85, 106, and 127 in subjects with active renal disease at baseline.

Additional possible exploratory efficacy outcomes include the following:

- median time to treatment failure as defined by:
  - death or need for additional immunosuppressive therapy, or
  - death, end-stage renal disease, doubling of serum creatinine, or SLE or renal flare;
- incidence at Days 22, 43, 64, 85, 106, and 127 of SLE flares using the SELENA and BILAG definitions;
- median time to first mild/moderate and severe SLE flares using SELENA and BILAG definitions;
- incidence at Days 22, 43, 64, 85, 106, and 127 of renal flares;

- median time to first renal flare;

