15.3.8. SELENA SLE FLARES

Occurrence of SELENA SLE flares will be recorded on the eCRF.

A mild/moderate flare is defined to include any of the following:

- increase in SLEDAI \geq 3 points, relative to baseline
- new/worse skin, stomatitis, serositis, arthritis, or fever
- increased prednisone < 0.5 mg/kg/day
- added NSAID/hydroxychloroquine
- increase in PhGA ≥ 1.0 , relative to baseline

A severe flare is defined to include any of the following:

- increase in SLEDAI ≥ 12 points, relative to baseline
- new/worse CNS-SLE, vasculitis, nephritis, myositis, platelet count $< 60,000/\mu\text{L}$, hemolytic anemia with hemoglobin < 7 mg/dL, requiring doubling > 0.5 mg/kg/day prednisone
- hospitalization for SLE
- prednisone > 0.5 mg/kg/day
- new immunosuppressive increase in PhGA to > 2.5 , relative to baseline

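### BILAG flares and the SLEDAI and PhGA items of SELENA flares are scored only against Day 1, so a return to entry level after improvement is not counted; add a Day 85 reference for Days 106 and 127

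*SAP*

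**What the plan says.** - **BILAG flare.** Protocol 6.2.2 has "BILAG severe flare: development of any new BILAG A domain score", and counts two or more new B scores as a flare. It does not say which visit makes a score new. SAP 15.3.9.1 supplies one: "A severe flare is defined as development of any new BILAG A domain score, relative to baseline", and "A moderate flare is defined as ≥ 2 new BILAG B domain scores, relative to baseline".
- **SELENA flare.** Protocol 6.2.2 gives the SLEDAI items as a change in score and the mild/moderate PhGA item as an increase, again with no reference visit. SAP 15.3.8 sets the mild/moderate SLEDAI item at a rise of at least "3 points, relative to baseline", the severe item at "increase in SLEDAI ≥ 12 points, relative to baseline", and ties the PhGA items to baseline. Other items carry no such anchor, for example "new/worse skin, stomatitis, serositis, arthritis, or fever" and "added NSAID/hydroxychloroquine". Any one item is enough, and occurrence is recorded on the eCRF.
- **Reference visits.** SAP 6.3 sets the efficacy baseline at Day 1 and end of treatment at Day 85. The last dose is on Day 64 (Protocol 4.1).
- **Timing and use.** Protocol 6.2.3.3 lists, among its additional possible exploratory outcomes, "incidence at Days 22, 43, 64, 85, 106, and 127 of SLE flares using the SELENA and BILAG definitions". The SAP analyses flare incidence as for SRI and adds Kaplan-Meier curves by treatment.
- **Deviations.** SAP 3.4 reports no meaningful departure from the protocol's analyses.

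**The concern.** Every subject enters with active disease (SLEDAI of at least 4). With Day 1 as the only reference, the more a subject improves, the further the disease must come back before these items register it. A subject who never improved is scored at the full sensitivity of 3 points. Days 106 and 127 fall 42 and 63 days after the last dose (106 − 64 and 127 − 64), which is where loss of effect would show. If active arms improve more and then lose the effect, these items would under-count relapse in those arms. That bears on the study's stated purpose, which is to provide experience for designing a larger efficacy study.

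**Working it through.** The documents give no power, event or detection figure for flares, so there is no stated figure to reproduce. The check is a count of paths, some threshold arithmetic, and a simulation on an assumed noise level.

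**1. BILAG, one domain, grades A to D.** Take every path that improves from Day 1 to Day 85 and then worsens. These are counts of paths, not of subjects.

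| Later grade | Paths | New against Day 1 | New against Day 85 |
|---|---|---|---|
| A | 6 | 3 (Day 1 grade B or C) | 6 |
| B | 5 | 1 clearly (C to D to B) | 5 |

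The three uncounted returns to A are those graded A on Day 1 (via B, C or D). Of the returns to B, two (B to C or D to B) are not new. Two more (A to C or D to B) are new only on a literal reading, which the SAP does not settle. A moderate flare needs two new B domains.

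**2. SLEDAI threshold.** Rise needed from Day 85 = fall by Day 85 + item threshold against Day 1.

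| Fall by Day 85 | Mild/moderate (≥ 3) | Severe, SAP (≥ 12) | Severe, protocol (> 12) |
|---|---|---|---|
| 4 (SRI minimum) | 7 | 16 | 17 |
| 6 | 9 | 18 | 19 |
| 8 | 11 | 20 | 21 |

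For 10 to 4 to 10, the change from Day 1 is 10 − 10 = 0, so neither item is met. The change from Day 85 is 10 − 4 = 6, which passes 3.

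**3. Chance that the 3-point SLEDAI item fires at one later visit.** Assumption: independent visit noise with SD 1.5 to 2 points, scores rounded, 400,000 draws. The SD is not in the documents.

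| True course | Against Day 1 | Against Day 85 |
|---|---|---|
| Fall 6, rise 6 | 12–19% | 89–95% |
| Fall 4, rise 6 | 41–43% | 89–95% |
| No fall, rise 4 (SD 1.5) | 76% | 76% |

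The 12–19% is noise alone, since that subject is truly back at the Day 1 level. These rates are for the SLEDAI item only, not for SELENA flare as a whole.

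**4. False alarms in a subject with no true change, same assumption.**
- At least one SLEDAI-item flare over the six post-baseline visits: 37–50% against Day 1, and 58–78% against the preceding visit.
- At least one at Days 106 or 127: 20–30% against Day 1, and 20–30% against Day 85.

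A preceding-visit reference therefore adds noise, and a Day 85 reference at those two visits does not.

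**5. What else would show the relapse.** The SAP fits an analysis of covariance to change from end of treatment for SLEDAI total, CLASI, the global assessments and joint counts (15.3.3 to 15.3.6). It assesses SRI and, by the same method, BILAG clinical response by visit. It plots BILAG grades and SLEDAI per subject (15.3.1.2, 15.3.4.2). All of these are group summaries or individual displays. BILAG receives no numeric score, its shift tables run from baseline, and change from end of treatment is not defined for it.

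**The case against.** The case against has four parts, and most of it stands.

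- **No contradiction with the protocol.** A reader might infer that the SAP overrides a protocol rule, because Protocol 6.2.2 names baseline in some definitions and not in the flare ones. The documents do not support this. The 4-point SLEDAI reduction in the protocol's SRI definition names no baseline either, yet plainly means from baseline. The SAP also reads new BILAG scores against baseline in its SRI derivation. It has filled a silence consistently, and SAP 3.4 is not shown to be wrong.
- **Not every flare is scored only against Day 1.** New or worse manifestations, added drugs, steroid increases and hospitalization name no baseline, so a SELENA flare can be recorded although the SLEDAI item is not met. Renal flares follow the protocol's own definition. A BILAG relapse to A in a domain that was B or C on Day 1 still counts.
- **Relapse after the last dose is not invisible.** The analyses in step 5 address group-level change after Day 85, and the subject plots would display A to C to A.
- **Limited reach.** Flares are additional possible exploratory outcomes in a study with 8 subjects planned per dose. Time to flare is estimated without a between-group test. Entry requires a SLEDAI score but no BILAG grade, so the number of subjects with an A domain on Day 1 is unknown.

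What remains is that 15.3.9.1 has no other limb to catch a return to entry level, and that no planned summary counts subjects who improved and then relapsed.

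**Conclusion.** The point holds in a limited form. For BILAG flares and for the SLEDAI and PhGA items of SELENA flares, Day 1 is the sole reference, so a return to the entry level after improvement is not scored by those rules. The path counts and thresholds follow from the SAP's wording alone; the detection and false-alarm percentages rest on the assumed SD of 1.5 to 2 points.

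A reader might go on to infer that the flare comparison is biased in favour of the drug. That would require the drug to work and then wear off, and the documents give no figure for either. They support only the conditional statement that, in that case, relapse would be under-counted most in the arms that improved most. This is a cheap improvement of low severity, affecting the interpretation of exploratory flare results and the design of the next study.

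**What to change.** - Keep the Day 1 flare analysis as planned, and say in SAP 15.3.8 and 15.3.9.1 that Day 1 is its reference visit.
- For Days 106 and 127, add a supplementary derivation against Day 85, the SAP's own end of treatment: new BILAG A and B scores, and SLEDAI and PhGA increases. Tabulate it by treatment. Derive it from the recorded scores, since the eCRF flare entry does not show which item was met.
- State whether an improvement from A to B counts as a new B, and put the PhGA increase on a stated scale: Protocol 6.2.2 gives it on 0 to 3, while SAP 15.3.5 describes 0 to 100 mm.
- SAP 15.3 limits exploratory analyses to on-treatment assessments; make clear that Days 106 and 127 are included.
- Do not use the preceding visit as the reference, because it raises noise-driven flares over repeated visits (step 4).

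The cost is SAP wording and one extra exploratory table. No new data are needed. The table covers only subjects with a Day 85 value and a later visit, because missing data are not imputed.
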